### **Background**

It is well documented that without reasonable access to safe abortion services, women risk their health and their lives to obtain clandestine abortions from unqualified persons in unhygienic conditions. According to the World Health Organization, 19 million women experience an unsafe abortion every year and 23.000 women die from complications of unsafe abortion each year. Globally, approximately 13% of all maternal deaths are due to complications of unsafe abortion. (Sedgh 2016). In low income areas in the world as a whole, an estimated seven million women every year are admitted to hospitals for treatment of complications from unsafe induced abortions (Singh, 2006). The indirect costs of unsafe abortion include the loss of productivity from abortion-related morbidity and mortality; the effect on children's health and education if their mother dies (an estimated 220.000 children worldwide lose their mothers every year from abortion-related deaths); and secondary infertility, stigma, and other socio-psychological consequences (Grimes DA, 2006).

### Medical abortion

In collaboration with WHO, medical abortion has been developed into a safe and effective method for induced abortion. Medical abortion with a combination of mifepristone and a prostaglandin analogue was first developed by our research group at the WHO-collaborating centre at the department of Obstetrics and Gynaecology, Karolinska Institutet and Karolinska University Hospital. It was introduced for clinical use in France in 1988, up to 49 days of gestation, in the UK in 1991 and in Sweden in 1992 up to 63 days of gestation. The sequential regimen of mifepristone (RU 486) followed one to two days later by the prostaglandin analogue misoprostol is used routinely for the termination of pregnancy in an increasing number of countries (von Hertzen et al., 2000, WHO, 1993, 2000, 2001). Medical abortion has the potential to reduce maternal mortality and morbidity if a simplified and demedicalized regimen is implemented. A medical abortion with mifepristone and misoprostol is a safe and effective method of abortion. When provided under supervised medical care, medical abortion has a success rate of approximately 95% to 98%. Very few serious complications result from medical abortions (WHO, 2006, 2012), RCOG, 2004). Even though mifepristone and misoprostol have been on the list of essential medicines of the WHO since 2005, there are still many countries where these medicines are not available (Gynuity Health Projects. 2007). Misoprostol is an orally active synthetic PGE1 analogue, which has become an important drug in obstetric and gynaecology because of its uterotonic and cervical priming action. It is safe, cheap, widely available and stable at room temperature. The effect is dependent on the dose as well as on the route of administration. Complications are rare during the initial 4-h period after misoprostol administration and do not warrant women to stay under medical supervision. Detailed counseling and information and the

possibility of receiving advice over telephone are likely to increase acceptability. Following our studies Swedish women now have the option to self administer misoprostol at home, which has had a major impact in Sweden as well as internationally (Fiala et al 2004, Kopp-Kallner et al., 2005). Following our study the recommendations from the Swedish Board of Health and Welfare changed and Sweden became the first European country to allow home-use of misoprostol in medical abortion. For women with an unwanted pregnancy who have decided on an abortion it is of major importance to avoid unnecessary waiting times. The possibility of home-use of misoprostol can contribute to this.

The updated guidance on Safe abortion technology by the World Health Organization (WHO 2012) emphasizes the simplifying or streamlining of abortion care to increase its access. It notes a high value on research to demedicalize abortion care, affirms that home use of misoprostol is a safe option for women, and it suggests the evaluation of internet provision and telemedicine, as further alternative service delivery channels of safe abortion, as a subject for future research.

### Women-on-web

Coincidently the public start of Internet (1991) happened at almost the same time as the introduction of medical abortion (1988). In the past 20 years Internet became a major source of information for people all over the world. As a consequence it is not surprising that women around the world started using the Internet to access information about abortion services. This reflected in the many discussion forums and online sales of misoprostol and/or mifepristone. In 2004, Women on Waves (a Dutch non-profit organization) was the first to publish instructions for women about "how to safely do an abortion yourself". A new project "Women on Web" was thereafter initiated to support women in countries where there are no safe abortion services. On the Women on Web website (www.wow.org), women can do an interactive web-based medical consultation. The interactive web-based questionnaire consists of 25 to 30 questions that serve to provide the women with information about the medical abortion and possible alternatives and identify contra-indications and risk factors for potential complications. A doctor reviews the answers to the online consultation. If there are no contraindications, a woman with an unwanted pregnancy up to 9 weeks gestation can receive a medical abortion with medication that is delivered to her home address. The medical abortion treatment consists of 200 mg mifepristone followed by 800 mcg misoprostol sublingually 24 hours later and 400 mcg misoprostol sublingually 4 hours thereafter. The package sent to the woman also includes a pregnancy test to be used 2 weeks after the abortion, to confirm that there is no ongoing pregnancy. Women are closely guided in the process through an email helpdesk in different languages.

Our studies have shown that telemedicine and provision of medical abortion through wow is safe, acceptable and with outcomes similar to medical abortion provided traditionally following face-to-face counselling (Gomperts et al., 2008, 2011, 2014, Grossman et al., 2011). Furthermore, recently home self-assessment of the abortion outcome through a low sensitivity U-hCG test and a checklist was shown to be highly accepted to women (Sunde Oppegaard et al., 2015, lyengar et al., 2015). In our study on home use of misoprostol a vast majority of women (99%) stated that they would also have preferred to administer mifepristone at home. However, according to the Swedish law medical abortion has to be performed in an approved health facility. The abortion is legally defined as being performed when mifepristone is swallowed. Thus, home use of misoprostol is allowed according to the law although the expulsion of the products of conception usually occurs following the administration of misoprostol.

To evaluate whether counselling through telemedicine is non-inferior to face-to face counselling a RCT will be conducted including women who chose medical abortion up to 63 days of gestation with home administration of misoprostol and self assessment of the outcome. The results of this study could be of major importance to increase access to safe abortion services. Telemedcine counselling has never been evaluated in a RCT.

### Material and Methods

# Hypothesis

Counselling through telemedicine will be as effective and safe as routine face-to-face counselling.

### **Objectives**

The overall aim of this project is to increase access to simplified medical abortion.

- To compare face-to face counseling with counseling through telemedicine in medical abortion with regard to efficacy (defined as complete abortion without on-going pregnancy or surgical intervention for incomplete abortion) evaluated 30 days after the abortion treatment based on patient follow up reports of low sensitivity uhCG, and patient records
- evaluation of safety, acceptability, surgical interventions, contraceptive uptake and unscheduled contacts.

# Design

Randomised controlled non-inferiority trial.

The study design is aligned with the CONSORT (Consolidated Standards of Reporting Trials), SPIRIT (Standard Protocol Items: Recommendations for Interventional Trials) and Medical Abortion Reporting of Efficacy (MARE) and Standardizing Abortion Research Outcomes (STAR)STAR recommendations.

### 1. Setting/Centres

The Department of Obstetrics and Gynaecology, Karolinska University Hospital/ Karolinska Institutet, Stockholm, Sweden. Following amendment new sites were added: SÖS, DS, Ultragyn.

### 2. Participants

Women requesting medical termination of pregnancy with home administration of misoprostol and home self-assessment of outcome of treatment, with pregnancies up to 63 days gestation (based on ultrasound dating).

### 3. Interventions

Women with an unwanted pregnancy, with no contraindication to medical abortion and self administration of misoprostol at home, of up to 63 days gestation, will be randomised into two groups at the time of the telephone booking:

# Group 1: intervention

Telemedicine counselling. Ultrasound and mifepristone at outpatient clinic, to be continued with home administration of misoprostol at 24-48 hours later and self assessment of outcome 2-3 weeks after mifepristone.

Group 2: Control

Routine appointment with the abortion clinic with face-to-face counselling, ultrasound dating and mifepristone at outpatient clinic, to be continued with home administration of misoprostol at 24-48 hours later and self assessment of outcome 2-3 weeks after mifepristone.

Both groups: Self assessment of outcome will be done by the hCG CheckTop test (Exelgyn/Veda Lab (Alençon, France) (Sunde Oppegaard et al., 2015 as used in clinical routine. A Follow-up online questionnaire to evaluate success of procedure and satisfaction with treatment, contraception uptake etc will be done approximately 2-3 weeks after mifepristone to evaluate success of procedure. An email or telephone reminder will be sent if the online contact is unsuccessful. The patient (electronic) records will be reviewed after 30 days in order to control for possible extra visits related to abortion-related complications.

### 4. Outcome measures

# Primary outcome

Efficacy of medical abortion defined as complete abortion without ongoing intrauterine pregnancy or surgical intervention for incomplete abortion within 30 days of the abortion treatment. The outcome will be determined based on the home low sensitivity uhCG and patient records (surgical intervention).

Secondary outcomes will include safety (AE/SAE), any additional medical treatment of incomplete abortion, bleeding days and estimated amount, infection, surgical treatment for other indications than ongoing pregnancy or incomplete abortion, unscheduled contacts and visits, acceptability with the abortion counselling and treatment (in-clinic or self managed, self reported /estimated gestational length and contraceptive choice.

Incomplete abortion will be defined as products of conception remaining in the uterus with continued bleeding, bulky uterus, and open cervix at examination, possibly necessitating surgical evacuation at the discretion of the provider or at the woman's request derived from patient records.

Adverse events (AEs) will be recorded. The completeness of the abortion and any AEs will be identified by the on line follow up and by clinical examination.

Data management will be organized locally by data entry personnel and at the WHO centre, Karolinska. Data will be entered by use of a clinical trial software, checked for accuracy, and corrected after consultation of clinical records and research assistants, and reviewed monthly by the Study Coordinator at the WHO centre with further checking of clinic records as necessary.

### Variables and measures

Abortions will be recorded as complete, incomplete, or failed (continuing pregnancy). A case record form (CRF) will be filled out for both groups (Group 1: telephone booking, online consultation, medication pick up, follow up (all done by the patient) and for Group 2: telephone booking, in clinic consultation (by the investigator), follow up. Data will be entered into an online password protected database (by the research midwife and investigator at each site), eCRF. The database will contain

demographic variables, gynecological history, ultrasound finding, contraceptive use, abortion treatment, any additional medical treatment or surgical intervention, unscheduled visits or contacts, bleeding and spotting (total number of days, amount in relation to menstruation), pain (less than, similar, or more than normal menstruation, pain medication enough, too much, too little), pain treatment, and acceptability (determined by responses to pretested questions).

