### Follow-up

A follow-up telephone call or web-based questionnaire to assess outcomes of treatment will be done by a nurse midwife or doctor approximately three weeks following the treatment (both groups). Women in the clinical routine group could choose to come back to the clinic for follow up. Appointments for postabortion contraception will be done as required.

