### Randomization procedure

Randomization: We will use a computer-generated randomization scheme with a varying block size. Randomization will be performed :1 by a midwife in the abortion clinic at the time of the first telephone consultation after the patient has been judged eligible for participation and has given her oral informed consent. Allocation to study group will be done after completion of a checklist of inclusion and exclusion criteria by opening consecutively numbered opaque, sealed, envelopes containing the randomisation group for each participant. Women will be identified through a patient log.

Women will be randomly assigned to either Group I) telemdicine counselling or Group II) standard face-to-face counselling. Women in group I will be given the address to a designated website and an appointment for ultrasound scan and pick up of medication while women in group II will be given an appointment to the abortion clinic. Medical abortion will be performed according to the Swedish national guidelines. Women will receive mifepristone (LinePharma, Paris, France) 200 mg orally at the clinic (counts as Day 1). Twenty-four to 48 hours later women self-administer 800 mcg misoprostol vaginally or sublingually (4 tabl Cytotec® 200 mcg, Pfizer, New York, USA). If bleeding has not started or is scant women will be advised to administer a second dose of 400mcg misoprostol sublingually 3 hours later. Follow-up will be done 2 weeks after treatment and outcome of abortion assessed primarily by low sensitivity urinary hCG test. The study will not be masked.

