### 8. Statistical analysis plan; power calculations - sample size

Sample size

The hypothesis to test is a non-inferiority hypothesis. The aim is to prove that telemedicine counseling is not inferior compared to standard abortion treatment. The expected efficacy rate (primary outcome) is 97.5% in both groups. The non-inferiority margin is set at 3%. The primary hypothesis will be tested by constructing a 95% confidence interval (CI) for the difference between the two treatments (intervention-control). If the upper limit of the CI is less than 3% the intervention will be declared as non-inferior to standard abortion care. In total 635 patients per group (1370 in total) is needed to obtain a power of 90%. To compensate for a 10% loss to FU an additional 138 women will be added to include 754 patients per group (total 1508 women).

Numbers and proportions of women having failed abortion and surgical intervention for incomplete abortion will be calculated by intervention. Both interventions will be compared using both absolute and relative measures with 95% confidence intervals. An intention-to-treat analysis as well as a per-protocol analysis will be performed. To evaluate the differences between the groups regarding independent nominal data such as side-effects and compliance, the chi squared test will be used. Continuous variables with a normal distribution, will be analysed using the Student's t-test whereas variable which are not normally distributed, such as age, GA (self-estimate vs LMP vs US) will presented as medians (range) and compared using Mann-Whitney U-test. Discrete numerical variables such as parity and bleeding days will be presented as means (range) and assessed for normality and comparison using the t-test or the Mann-Whitney U-test. Numeric variables (time lost from work and number of unplanned visits/consultations) will be analysed using analysis t-test. Results will be considered statistically

significant if P-value < 0.05. An independent data and safety monitoring committee will evaluate AE/SAE and make decisions if the trial should be stopped or continue as planned. Reason for stopping the trial could be a high failure rate or low acceptability rate in the intervention group. The plan for analysis and the study protocol has been developed in collaboration with prof. [name], Statisticon AB.

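### Bleeding days is analysed as a complete total, although women still bleeding at the 2-to-3-week follow-up can give only a cut-off count

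*Combined protocol and SAP*

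**What the plan says.** Section 4 (Outcome measures) lists "bleeding days and estimated amount" among the secondary outcomes. Under Variables and measures the item appears as "bleeding and spotting (total number of days, amount in relation to menstruation", that is, one number of days per woman plus an amount. Section 8 states: "Discrete numerical variables such as parity and bleeding days will be presented as means (range", followed by a t-test or a Mann-Whitney test. It names no method for incomplete durations.

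The patient-reported follow-up is dated three ways:

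- Section 3 (Interventions, paragraph on both groups): the online questionnaire "will be done approximately 2-3 weeks after mifepristone to evaluate success of procedure".
- Section 6, Follow-up: a telephone call or web questionnaire "approximately three weeks following the treatment (both groups".
- Randomization procedure: "Follow-up will be done 2 weeks after treatment".

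Two further statements affect when a woman answers. Section 3 adds: "An email or telephone reminder will be sent if the online contact is unsuccessful". It gives no last date. The Follow-up section adds: "Women in the clinical routine group could choose to come back to the clinic for follow up". The only later step is a review of patient records after 30 days, aimed at extra visits. The documents describe no bleeding diary, no date of last bleeding, no answer option for continuing bleeding and no fixed counting period.

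**The concern.** A total is known only once bleeding has ended. If the question is put two to three weeks after treatment, a woman who is still bleeding can report only the days so far. The stated analysis has no way to tell that count from a completed one, and the 30-day record review is not described as collecting bleeding duration.

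Two consequences follow. First, the longest durations are shortened most, so both arm means are too low and a real difference between arms looks smaller than it is. Second, the recorded count of a woman still bleeding grows with the date on which she is asked. If the arms were asked at different times on average, that difference in timing would show up as a difference in bleeding. What is at stake is one patient-relevant secondary outcome; the primary efficacy comparison does not use it.

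**Working it through.** **Inputs.** The plan gives no figure for bleeding days, so there is none to reproduce. From the documents: contact at c = 14 or 21 days, and 754 women per arm less 10% loss, 754 × 0.90 = 678.6, taken as 679. Assumed, because the documents are silent: duration T is log-normal with median m and log-SD s.

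**1. Share still bleeding at contact.** 1 − Φ(z), with z = ln(c/m)/s.

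| c | m | s | z | still bleeding |
|---|---|---|---|---|
| 14 | 10 | 0.4 | 0.84 | 20% |
| 14 | 16 | 0.4 | −0.33 | 63% |
| 21 | 10 | 0.4 | 1.85 | 3% |
| 21 | 16 | 0.6 | 0.45 | 33% |

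These are the extremes for m from 10 to 16 and s from 0.4 to 0.6. With shorter bleeding (m from 7 to 9) the shares fall to 4-23% at day 14 and 0.3-8% at day 21.

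**2. Effect on the mean.** The recorded value is the smaller of T and c. Its mean is M·Φ(z − s) + c·(1 − Φ(z)), where M = m·exp(s²/2) is the true mean. For m = 13 and s = 0.6, M = 15.56 days.

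- Day 14: 15.56 × 0.317 + 14 × 0.451 = 4.93 + 6.31 = 11.24 days.
- Day 21: 15.56 × 0.579 + 21 × 0.212 = 9.01 + 4.45 = 13.46 days.

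Moving the contact by one week shifts the recorded mean by 13.46 − 11.24 = 2.22 days. For m from 7 to 9 the shift is only 0.1 to 1.0 days.

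**3. Effect on a true difference, same contact day in both arms.** With medians 13 and 15 and s = 0.5:

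| | mean, median 13 | mean, median 15 | difference |
|---|---|---|---|
| complete durations | 14.73 | 17.00 | 2.27 |
| cut at day 21 | 13.52 | 14.93 | 1.41 (62% kept) |
| cut at day 14 | 11.52 | 12.22 | 0.70 (31% kept) |

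For m from 9 to 16, s from 0.4 to 0.6 and counts stopping the day before contact (13 or 20 days), a day-14 contact keeps about 12-61% of the true mean difference and a day-21 contact about 36-92%.

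**4. Effect on the tests, same contact day, 679 per arm (simulation).** With no true difference, the false-positive rate stays at 4-6%. For a one-day difference in medians (m from 9 to 14), t-test power falls by 0 to 16 percentage points at day 14 (worst case 87% to 71%) and hardly at all at day 21. For medians 13 and 14 with s = 0.5, Mann-Whitney power is about 77% with complete durations, 74% cut at day 21 and 69% cut at day 14. The loss is far smaller than the shrinkage of the mean because cutting the long tail also reduces the variance.

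**5. Different contact days between arms, no true difference.** The false difference equals the gap in the share asked late times the one-week shift. If 70% of one arm and 40% of the other are asked at day 21 and the rest at day 14, then for m = 13 and s = 0.6 it is 0.30 × 2.22 = 0.67 days. For m from 9 to 16 the simulated false difference is about 0.2 to 1.1 days. For m from 9 to 14 the false-positive rate is 16-99% (t-test) and 7-96% (Mann-Whitney). The 70% and 40% are illustrative; no such split is in the documents.

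**The case against.** The bleeding items themselves are not reproduced. Variables and measures lists what the database holds, and only the acceptability questions are explicitly tied to follow-up. The form may already carry a stop date or a completion date. A reader might infer that the plan says bleeding is asked once; it does not. This is a fair inference from the single follow-up contact described, and no more. It stands as a limit on certainty. It does not rescue section 8, which provides no analysis for a woman whose bleeding has not ended.

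A reader might also infer that the design will create a false difference between arms. The documents do not support that. The follow-up schedule is the same for both groups, the reminders apply to both, and with a common contact day the error rate is nominal. The one documented asymmetry is the optional clinic return in routine care, and no section puts that visit on a different date. Unequal timing is a risk left open, not a planned feature.

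A third tempting reading is that the women cut off are the treatment failures. Section 4 does name continued bleeding in its definition of incomplete abortion, but together with retained products and examination findings taken from records. Surgical intervention for incomplete abortion is captured by the primary outcome to 30 days. Expected failure is 2.5% (100% − 97.5%), so nearly all women still bleeding at two weeks under the assumed durations would not be failures.

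Finally, both arms receive the same drug regimen and the loss of power is small. That is correct, and it limits the weight of the point. The bias in the reported mean and in the estimated difference remains.

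**Conclusion.** The point holds in a limited form. The stated analysis takes a possibly cut-off count as a complete total, and the cut-off date itself is given three ways. For any woman still bleeding at contact, the recorded count is too low; this follows from the design without any outside figure. How much it matters rests wholly on assumed durations. At median 13 days and log-SD 0.6, a true mean of 15.6 days is read as 11.2 or 13.5. With medians of 7 to 9 days the effect is much smaller, and at a day-21 contact slight.

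The planned tests keep most of their power, and a spurious difference depends on unequal timing that the documents allow but do not prescribe. Nothing here touches the non-inferiority conclusion on efficacy. It is a cheap improvement to a secondary outcome, with medium confidence because the questionnaire cannot be seen.

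**What to change.** 1. Reconcile the three statements of follow-up timing (section 3, the Follow-up section and Randomization procedure) to one window counted from one stated starting point. Apply it equally to both arms, including women who return to the clinic and those who answer after a reminder.
2. Store the date of the contact, and ask for the date of last bleeding or whether bleeding continues that day.
3. Analyse time from treatment to end of bleeding, censoring women still bleeding at the contact date, with Kaplan-Meier curves and a log-rank test. Keep the total count as a descriptive summary, reported with the number still bleeding in each arm.

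Limiting the count to the first 14 days looks like a simpler remedy but is not one. It imposes the day-14 cut on everyone (2.27 days becomes 0.70 in the example), discards later information, and cannot be complete for every woman at a 2-week contact because misoprostol follows mifepristone by 24-48 hours.

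Cost: one extra questionnaire item, one stored date and a sentence in section 8, with no added contact. The downside is that time to last bleeding differs slightly from total bleeding days when bleeding is intermittent, which is why the count is kept as a description.
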